A screening log will be maintained by research coordinators of all patients who were considered for enrollment and their demographics, clinical characteristics and the reason for their exclusion.

Sample Size

Our primary outcome is the CATH rate at 3 months. Based on our previous analyses from our IRB 2016-157 study (the FFR-ACP study), the SOC arm had a 89.5% CATH rate in the 71-99% stenosis group and 58.3% in the 51-70% stenosis group. With the 51-70% stenosis group having twice as many patients as the 71-99% group, we anticipate 68.7% of CATHs in all SOC controls. In our previous CT-FFR negative patients, there were 65.6% CATHs in the 71-99% stenosis group and 21.3% in the 51-70% stenosis group. Again with a 2 to 1 ratio, we anticipate an overall CATH rate of 36.1% in the FFR patients. Since these are estimates for the FFR group, we calculated several possibilities. All have 90% power with a significance level of 0.05%.

We determined a sample size of 87 patients per arm are needed to detect this difference. We intend to randomize 100 patients per arm to adjust for any lost to follow-up. We used PASS 15 Power Analysis and Sample Size Software (2017). NCSS, LLC. Kaysville, Utah, USA, ncss.com/software/pass.

Numeric Results for Testing Two Proportions using the Z-Test with Unpooled Variance

H0: P1 - P2 = 0. H1: P1 - P2 = D1 ≠ 0.

Target	Actual						
Diff							
Power	Power*	N1	N2	N	P1	P2	D1
Alpha							
0.90	0.90148	44	44	88	0.6870	0.3600	0.3270
0.0500							
0.90	0.90458	59	59	118	0.6870	0.4000	0.2870
0.0500							

0.90	0.90155	87	87	174	0.6870	0.4500	0.2370
0.0500							

* Power was computed using the normal approximation method.

Randomization

We intend to include 200 patients (100 per arm). Patients will be randomized in a 1:1 ratio to Standard of Care (SOC) or CT-FFR-guided management, in alternating block design to ensure equal groups periodically. The order of randomization will be generated using SAS for Windows 9.3, Cary, NC. Randomization envelopes will be generated by a Beaumont Research Biostatistician and will be opened in sequential order. Once the patient has met all the inclusion criteria, none of the exclusion criteria and has signed the informed consent, the next envelope will be opened which will contain a slip indicating the patients assigned study number and to which arm they are being randomized.

SOC Group Management

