Attending physicians will dictate SOC management according to their own clinical judgment. This could include discharge without further testing, EKG-only stress testing, stress echocardiography, stress myocardial perfusion imaging, direct admission and further noninvasive testing or CATH. In addition to standard testing, a blinded CT-FFR will be obtained for post hoc analysis, but it will not be used for patient management. Image data from our CT workstation will be sent directly to HeartFlow, Inc. over a secure research transfer node.

If attending physicians decide that SOC Group patients should undergo CATH, the protocol will specify an invasive fractional flow reserve will be performed on all lesions over 30% stenosis severity, to confirm the presence or absence of flow-limiting stenosis. This may be waived without protocol deviation if deemed unsafe by the severity of stenosis or due to clinical circumstances, as documented in a completed Physician Study Questionnaire.

CT-FFR-Guided Group Management

Patients in this group will be triaged using CT-FFR. Image data from our CT workstation will be sent directly to HeartFlow, Inc. over a secure Priority (STAT) transfer node. Interpreting physician will categorize CT-FFR results as follows:

1. CT-FFR >0.80. All CT-FFR segmental values are >0.80, with no indication of flow limiting ischemia. A non-binding recommendation that the patient undergo an initial trial of medical therapy will be made by the interpreting co-investigator. Attending physicians will be asked to complete a study Physician Questionnaire to determine whether they followed this recommendation or not, and if not, why not.
2. CT-FFR 0.70-0.80. These will be reported as values in the abnormal range without specific recommendations about whether CATH should be performed. Attending physicians will decide triage in consideration with other clinical data. Attending physicians will be asked to complete a study Physician Questionnaire to determine what clinical factors influenced their triage decision.

3. CT-FFR <0.70. These are abnormal values that are will be reported as high-risk. A non-binding recommendation that the patient undergo CATH will be made by the interpreting co-investigator. Attending physicians will be asked to complete a study Physician Questionnaire to determine whether they followed this recommendation or not, and if not, why not.

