Risks Associated with Heart Catheterization and Invasive Fractional Flow Reserve

Common (more than 10%)

- warm feeling or flushed feeling during adenosine infusion (which is part of the FFR study)
- lightheadedness
- nausea
- pain
- discomfort
- bruising or bleeding where the catheter is inserted in the groin
- radiation equivalent to 3-5 years of natural background radiation

Rare (less than 1%)

- contrast (dye) allergy
- diaphoresis (temporary excessive sweating)
- atrioventricular block -impaired conduction of the impulse that regulates the heartbeat (from adenosine)
- contrast induced nephropathy (deterioration of kidney function due to contrast exposure)
- hives (for those allergic to contrast dye)
- thrombosis (blood clots resulting in reduced blood flow)
- artery dissection (damage to the artery wall)
- perforation (a hole in the artery)
- stroke
- myocardial infarction (heart attack)
- death

Internal Safety Monitoring Committee

An Internal Safety Monitoring Committee will conduct regularly scheduled reviews of the safety of patients. Two physicians and a statistician who are not co-investigators will be included. Members will monitor safety outcomes, enrollment and completeness of follow-up. The Committee will meet after the first 20 patients and after each 40 subsequent patients till the study is completed. Any MACE event or major adverse outcome will be reported immediately to the Committee. The results of all Committee meetings will be provided to the IRB.

Data Analysis

Descriptive statistics will be given for all variables collected including indications for the test, demographics, patient history, CTA tech information, details from the physicians reading form, and from the CT-FFR. Missing data will remain missing and will not be replaced by substitutions or interpolation. Categorical variables will be summarized as counts and percentages. All continuous variables will be

summarized as means+/- the standard deviation where normal or median and 25th, 75th percentiles if not normal. The minimum and maximum will also be provided.

Catheterization Rate: The primary outcome will be examined between the 2 randomization arms using Pearson's Chi-square test. The Odds ratio and 95% confidence interval will also be reported.

Diagnostic Effectiveness: The secondary outcome will be defined as the proportion of accurate triage using CATH-FFR as the gold standard among all patients triaged to CATH by each strategy.

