The SOC group will be analyzed according to actual triage decisions, as well as the hypothetical results of triage using a blinded CT-FFR analysis collected on those patients. The accuracy of triage between these two methods will then be compared.

Safety: The secondary outcome will be safety, as defined by the incidence of death, ACS or late unscheduled revascularization in each group.

Additional data analysis:

The Total length of stay, with sub-analysis of ED and inpatient length of stay will be reported as medians, 25th and 75th percentiles and minimum to maximum. The 2 randomization arms will be examined for each of these using Wilcoxon rank sum tests.

The hospital admission rate, the proportion of patients going to CATH in either arm who are found to have significant coronary stenosis (>50 stenosis), proportion of patients going to CATH who have a positive invasive FFR, percentage of patients undergoing PCI or CABG within 3 months, secondary diagnostic testing during index visit or within 3 months follow-up, including: recurrent ED visits, inpatient admissions for suspected acute coronary syndromes and/or CATH, outpatient or inpatient evaluation with cardiac CCTA or stress testing, cardiac surgery or PCI and MACE events (including all cause death, acute myocardial infarction, acute coronary syndromes, unscheduled revascularization after index visit) will be examined between the 2 arms using Pearson's Chi-square test where appropriate (Expected frequency>5 in all cells), otherwise Fisher's Exact tests will be used. The Odds ratios and 95% confidence intervals will also be reported.

[figure not shown]
Estimated costs of care: including all estimated charges based on Beaumont hospital analysis multiplied by the standard Medicare cost/charge ratio will be reported as medians, 25th and 75th percentiles and minimum to maximum. The 2 randomization arms will be examined using Wilcoxon rank sum tests.

We may explore possible associations between patient characteristics demographics, prior history or testing indications and the randomization groups, safety outcomes,

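### Costs are to be compared only by medians and a Wilcoxon test, so mean cost per patient and its difference between arms would never be estimated, and the gap between medians could misstate the saving

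*Combined protocol and SAP*

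**What the plan says.** The cost paragraph stands in the Data Analysis section, among the additional analyses. Each patient's cost is the estimated hospital charges "multiplied by the standard Medicare cost/charge ratio will be reported as medians, 25th and 75th percentiles and minimum to maximum". The comparison between arms is one sentence: "The 2 randomization arms will be examined using Wilcoxon rank sum tests".

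The general rule earlier in the same section does not add a mean. Continuous variables are "summarized as means+/- the standard deviation where normal or median and 25th, 75th percentiles if not normal", so a mean is produced only for a variable judged normal. Cost has its own rule in any case.

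The Sample Size section gives the catheterization rates on which the trial is planned. For SOC, "we anticipate 68.7% of CATHs in all SOC controls". For CT-FFR, "we anticipate an overall CATH rate of 36.1% in the FFR patients", with 36%, 40% and 45% used in the power table. Risks of the Study gives other figures from the centre's own experience: 58% before CT-FFR came into use, and 79/147 (54%) with it.

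Under SOC Group Management, every SOC patient also has the test for research: "a blinded CT-FFR will be obtained for post hoc analysis, but it will not be used for patient management". The cost paragraph does not say whether this charge, or the charge for the clinical CT-FFR in the other arm, is counted.

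**The concern.** A hospital or payer asking whether CT-FFR saves money needs total cost divided by number of patients, that is, the arithmetic mean per arm and the difference between the means. Medians do not give this, and a rank sum test estimates no amount of money.

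The median may serve especially poorly here. Catheterization is likely to be a main driver of cost, and the planned rates put more than half of SOC and fewer than half of CT-FFR patients in the catheterized group. The two medians could then compare a typical catheterized patient with a typical non-catheterized one, although the arms differ in catheterization for only about a quarter to a third of patients. A reader could take the gap between medians for the saving per patient.

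**Working it through.** **Planning rates.** The inputs are the stratum rates in the Sample Size section: "the SOC arm had a 89.5% CATH rate in the 71-99% stenosis group and 58.3% in the 51-70% stenosis group", and for CT-FFR 65.6% and 21.3%, weighted 2:1 towards the 51-70% stratum.
- SOC: (2 × 58.3 + 89.5)/3 = 68.7%, as stated.
- CT-FFR: (2 × 21.3 + 65.6)/3 = 36.07%, stated as 36.1%.

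The plan contains no cost figure to reproduce.

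**Where the medians fall.** Suppose every catheterized patient costs more than every other patient. With 100 per arm, the arm median then depends on which group is the majority. Binomial probabilities:
- SOC at 68.7%: catheterized majority (51 or more), 0.9999.
- CT-FFR: no catheterized majority (50 or fewer), 0.998 at 36.1%, 0.98 at 40%, 0.87 at 45%.
- At the rates in Risks of the Study: catheterized majority, 0.94 at 58% and 0.76 at 54%.

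The medians very probably fall in different groups at the planning rates. At the historical rates both most likely fall among catheterized patients.

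**Limiting case, no spread within a pathway.** Let the cost be 1 without and R with catheterization. The difference in means is (p1 − p2)(R − 1). If the medians fall on opposite sides, their difference is R − 1, and the ratio of the two is 1/(p1 − p2):
- 68.7% vs 36.1%: 1/0.326 = 3.1.
- 68.7% vs 45%: 1/0.237 = 4.2.
- 58% vs 54%: both medians equal R, so their difference is 0 while the means differ by 0.04(R − 1).

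**With spread (assumed values).** Lognormal cost in each pathway, mean 1 without and R with catheterization, R = 2-4, common CV 0.3-1.0, log-SD s = √ln(1 + CV²). The arm mean is 1 + p(R − 1). The arm median m solves (1 − p)Φ[(ln m + s²/2)/s] + pΦ[(ln m − ln R + s²/2)/s] = 0.5. The CT-FFR charge is left out.

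Example, R = 3, CV 0.3, 68.7% vs 45%: means 2.374 and 1.900, difference 0.474 (20.0%); medians 2.406 and 1.403, difference 1.003 (41.7%); ratio 1.003/0.474 = 2.12. With CV 1.0 the medians are 1.544 and 1.149, difference 0.395, ratio 0.395/0.474 = 0.83.

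Difference in medians divided by difference in means, 68.7% vs 45%:

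| R | CV 0.3 | CV 0.5 | CV 0.8 | CV 1.0 |
|---|---|---|---|---|
| 2 | 1.46 | 1.08 | 0.87 | 0.77 |
| 3 | 2.12 | 1.36 | 0.97 | 0.83 |
| 4 | 2.52 | 1.62 | 1.07 | 0.90 |

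At 68.7% vs 36.1% the range is 0.74 to 2.05. Over both planning pairs it is therefore about 0.7 to 2.5. At 58% vs 54% it is 0.77 to 2.31, but of a small amount: the mean saving is 0.04 × (R − 1), or 0.04 to 0.12 of a no-catheterization cost.

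As a percentage of the SOC figure, the median saving exceeded the mean saving in all 36 scenarios (three rate pairs, three values of R, four CVs). The direction thus depends also on whether the saving is quoted in money or in percent.

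**Effect of a charge for CT-FFR.** A fixed charge for every CT-FFR patient moves that arm's mean and median by the same amount. If it exactly cancels the mean saving (0.474 in the example), the medians still show 1.003 − 0.474 = 0.529 in favour of CT-FFR at CV 0.3. At CV 1.0 they show 0.395 − 0.474 = −0.079, an apparent extra cost.

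**The case against.** A reader might infer that the planned analysis is bound to favour CT-FFR. The documents do not support that.
- They give no costs, cost ratio or spread. The large ratios above need tight costs within each pathway, yet a catheterization pathway here runs from a diagnostic procedure alone to PCI or CABG. With wide spread, the absolute difference in medians is mostly below the difference in means.
- The placement of the medians depends on the planning rates. The CT-FFR figure rests on a selected group, "In our previous CT-FFR negative patients, there were 65.6% CATHs in the 71-99% stenosis group and 21.3% in the 51-70% stenosis group", so the rate for the whole arm may be higher, and the 58% and 54% figures put both medians above the divide. The 54% cohort had stenosis of 25-99%, so it does not match this trial exactly either.
- A median is not biased for what it estimates, and the Wilcoxon test estimates no saving at all. A fixed CT-FFR charge is not hidden by the median, since it raises both measures equally.
- The protocol states no mean-cost aim. Cost is in neither the objective nor the primary and secondary hypotheses.

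All of this stands, and it limits both the claim and its weight. It does not supply the missing estimate. If the size and sign of the discrepancy depend on unknown costs, that is a reason to estimate the mean difference directly.

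**Conclusion.** The point holds in a limited form. It is certain from the text that the plan yields no mean cost per patient, no mean difference and no confidence interval for a cost difference. At the planning rates the medians can fall on opposite sides of the catheterization divide, and the gap between them could misstate the saving and may overstate it. Under cost ratios of 2-4 and CVs of 0.3-1.0, all assumed, it is about 0.7 to 2.5 times the mean difference. Size and direction remain open, because no costs are given and the document's two sets of catheterization rates lead to different placements.

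Severity is low. The primary outcome, safety and sample size are untouched. This is a free improvement to an additional analysis.

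**What to change.** In the cost paragraph, make the comparison the difference in arithmetic mean cost per patient between the randomized arms, with a bootstrap 95% CI, and report both arm means. Keep medians, quartiles and range as description; the Wilcoxon test may stay as a supplement.

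Add two counting rules: the CT-FFR charge is included for the CT-FFR arm, and the research-only blinded CT-FFR is left out of SOC costs. If it were counted in SOC, the charge for the test under study would cancel out of the comparison.

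The cost is a few lines of wording and code. The per-patient costs are already to be derived, so no new data are needed.

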True negative case: CT-FFR negative and CATH-FFR negative

Proportion of correct CT-FFR triage = (True positive + True negative) / All CATH

SOC group:

True positive case: SOC chosen by attending physician for CATH confirmed by CATH-FFR. By definition, the clinicians' decision to CATH based on clinical evidence is considered an SOC positive case, there can be no SOC true negative cases that go to CATH.

Proportion of correct SOC triage = True positive / All CATH

2. Safety: Patients following CT-FFR-guided management will have similar MACE rates, including death, ACS and unanticipated late revascularization when compared to SOC-guided patients.

Methods

Study Population

The study population will be drawn from ED ACP who have already undergone CCTA for diagnosis, and have been found to have 50% or greater stenosis but less than 90% of at least one coronary branch. Two-hundred patients meeting entry criteria will be enrolled from a sample of ED ACP patients at Beaumont Hospital (Royal Oak). These patients will be randomized 1:1 using sealed envelopes provided by the study statistician, to either standard of care (SOC) or CT-FFR management. (See Figure 1. Study Diagram)

Inclusion Criteria

1. Emergency department or inpatients admitted through the ED with chest pain suspicious for ACS based on history and physical examination.
2. At least one biomarker (troponin) and electrocardiogram with no evidence of definite ACS.
3. A completed CCTA demonstrating $\geq 50\%$ but $< 90\%$ stenosis of at least one coronary artery branch.
4. CCTA test images with sufficient diagnostic quality for CT-FFR analysis.
5. Ability and willingness to provide informed consent.

Exclusion Criteria

- 1 Left main coronary stenosis of 50% or greater.
- 2 CCTA lesions demonstrating stenosis >90% ("subtotal"), or complex, high-risk plaque characteristics resulting in an a priori recommendation for triage to CATH by CCTA interpreting physician.
- 3 Attending physician a priori decision for CATH.
- 4 Prior coronary stent, coronary bypass or prior known myocardial infarction.
- 5 Clinical instability, such as hypotension, signs of shock, and/or unrelieved or accelerating chest pain.
- 6 Pregnancy

Obtaining Consent

Consent will be obtained by a co-investigator. Patients will have at least 20 minutes to consider whether they wish to consent.

Screening Log

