or events using contingency table methods, t tests or Wilcoxon Rank Sum, as appropriate. Associations between radiation dose/efficiency and patient characteristics may be explored with nonparametric methods. We may also explore possible relationships between the CTA stenosis categories (0%, 1-49%, 50- 100%) and the CT-FFR final test results categories and CATH and revascularization results. The occurrence of clinical events recorded at the 3 month chart review and structured patient questionnaire will be related to the category of final noninvasive results (Normal, Probably Normal, Equivocal, Probably Abnormal and Abnormal) using methods for contingency tables which incorporate the natural ordering of test categories. Odds ratios (ORs) with associated 95% confidence intervals (CIs) may be shown relating the occurrence of safety outcomes to test response categories with the normal category as the reference point.

Analysis will be completed by a Beaumont Research Institute biostatistician using The SAS System for Windows version 9.3 (or higher).

Figure 1 - Study Diagram

[figure not shown]

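### Three-month events are to be related to a five-level result scale that the plan never defines, and an optional analysis uses stenosis bands that put every patient in the same band

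*Combined protocol and SAP*

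**What the plan says.** Three statements near the end of Data Analysis, among the additional analyses, matter here.

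- **Stenosis bands (optional):** "We may also explore possible relationships between the CTA stenosis categories (0%, 1-49%, 50- 100" per cent), set against CT-FFR result categories, CATH and revascularization.
- **Events by test result (stated as planned):** events from the 3-month chart review and questionnaire "will be related to the category of final noninvasive results (Normal, Probably Normal, Equivocal, Probably Abnormal and Abnormal", using contingency-table methods that respect the ordering.
- **Odds ratios (optional):** these may be shown "relating the occurrence of safety outcomes to test response categories with the normal category as the reference point".

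Other sections fix who is enrolled and how results are classified.

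- **Study Population:** patients "have been found to have 50% or greater stenosis but less than 90% of at least one coronary branch".
- **CT-FFR-Guided Group Management:** three result categories. The first is above 0.80: "All CT-FFR segmental values are >0.80, with no indication of flow limiting ischemia". The second is "CT-FFR 0.70-0.80. These will be reported as values in the abnormal range without specific recommendations about whether CATH should be performed". The third is below 0.70, reported as abnormal and high-risk.
- **SOC Group Management:** the attending physician may choose among several tests or none. A blinded CT-FFR is also obtained.
- **Hypotheses:** subset analysis of the primary outcome in stenosis groups 51-70% and 71-90%.

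**The concern.** The event analysis is a commitment, but its explanatory variable is not defined anywhere in the document. The analyst would have to decide which test counts as the final noninvasive result, how it is graded into five levels, and who forms the reference group. That choice could be made after the events are known, which a plan should prevent.

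The stenosis split has a different fault. It is fully specified, but under the trial's own entry criteria it does not vary between patients.

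What is at stake is modest but relevant. The plan attaches a non-binding recommendation for initial medical therapy to CT-FFR above 0.80, and the Appendix argues from earlier revascularization data that this will be safe. The safety and MACE analyses compare randomized arms. A clear, prespecified description of 3-month events by CT-FFR result would speak directly to that argument, and the present wording does not deliver one.

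**Working it through.** The plan gives no figure on this point to reproduce. The sample size (87 per arm required, 100 per arm to be randomized) concerns the CATH rate and does not enter the check.

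**1. Stenosis bands against the entry criteria**

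Inputs: stenosis of at least 50% and under 90% (Study Population, Inclusion Criteria); bands 0%, 1-49%, 50-100% (Data Analysis); groups 51-70% and 71-90% (Hypotheses). Each patient is classified by the worst lesion, in whole per cent.

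Admissible values run from 50 to 89, so there are 89 − 50 + 1 = 40.

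| Grouping | Admissible values in each group |
|---|---|
| 0% / 1-49% / 50-100% | 0 / 0 / 40 |
| 51-70% / 71-90% / neither | 20 / 19 / 1 (exactly 50%) |

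With the first grouping, 40/40 = 100% of eligible patients are in one band, so the 200 planned patients split 0 / 0 / 200. A table of occupied bands by the three CT-FFR categories has (1 − 1) × (3 − 1) = 0 degrees of freedom, so no association can be estimated.

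The second grouping varies. The counts above are admissible values, not expected patients. The Sample Size section assumes twice as many patients at 51-70% as at 71-99%. If that ratio held here, 200 × 2/3 ≈ 133 patients would be in the lower group and 200 × 1/3 ≈ 67 in the upper. The upper group could be smaller, because this trial stops below 90%.

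**2. The five-level scale against each test it might describe**

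| Candidate source | What the plan provides | Does it yield the five levels? |
|---|---|---|
| CCTA | Every patient has at least 50% stenosis | A normal reference cell would be empty |
| CT-FFR | Three categories; 0.80 or below is abnormal | Abnormal has a counterpart, and >0.80 is its natural complement; no rule gives the three levels between |
| Stress testing in SOC | Several modalities, or no further test | No common grading stated; some patients may have no result |
| Physicians' reading form | Named as a data source in Data Analysis; not reproduced | Cannot be judged; the analysis text does not refer to it |

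No row supplies a stated scale of five levels that applies to both arms.

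**3. Which statements are binding**

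Relating events to the five categories is stated as planned. The odds ratios against normal and the stenosis exploration are optional.

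**4. Whether a repair needs new data**

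CT-FFR is to be obtained in both arms (blinded in SOC), CCTA stenosis is an entry criterion, and 3-month events are already followed. No new data item is needed.

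**The case against.** The strongest reply is that these are drafting gaps in peripheral analyses and should not be read for more than that. Several stronger readings are tempting, and the documents do not support them.

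- **That the trial does not produce the five categories.** The term used is wider than CT-FFR, and the reading form is not in the documents. A five-level field on it cannot be excluded. Only the absence of a definition is shown.
- **That odds ratios against normal cannot be computed.** This follows only if normal means a normal CCTA. A stress test, or CT-FFR above 0.80, can be normal in a patient with 50-89% stenosis. The odds ratios are optional in any case.
- **That none of the five levels matches a CT-FFR category.** The plan itself calls values of 0.80 or below abnormal. What is missing is a mapping to five levels.
- **That the plan loses its only analysis of CT-FFR result against outcome.** An optional analysis relates CT-FFR categories to CATH and revascularization. It does not name death or ACS.
- **That the wording was carried over from a broader population.** The earlier registry work did include lower stenosis, but the plan does not say where the wording came from, and the point does not need it.

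The stenosis point is also limited to patient level. Eligibility needs only one qualifying branch, so a per-vessel or per-lesion analysis could fill the lower bands. The plan describes no such analysis and does not state the unit.

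These limits stand. They do not supply the missing definition, and they do not restore a contrast between patients.

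**Conclusion.** The point holds, with minor weight.

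- **Stenosis bands:** wrong as written at patient level. All eligible patients fall in one of three bands. This assumes classification by worst lesion.
- **Five-level scale:** not defined for this trial. Five levels are named, three CT-FFR levels are defined, and no mapping or common scale across arms is given. This rests on the documents as supplied, without the reading form or the figures.

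The effect is limited to additional analyses, one stated as planned and the others optional. The CATH-rate comparison, the diagnostic-effectiveness and safety analyses, and the sample size do not change.

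**What to change.** 1. Replace the five levels with the three CT-FFR categories (>0.80 as reference, 0.70-0.80, <0.70). The plan already intends methods that use the ordering, so an ordered trend test fits.
2. Apply the same categories to the blinded CT-FFR in SOC. Show results separately by arm, or stratify by arm, because CT-FFR guides care in one arm and is unseen in the other. Simple pooling would mix the test's prognostic value with the effect of acting on it.
3. State that the analysis is descriptive, since events may be few, and report event counts per category.
4. Replace the stenosis bands with the groups under Hypotheses (51-70%, 71-90%). Assign exactly 50% to the lower group, and state that the patient's worst lesion is the unit.
5. If a five-level field does exist on the reading form and is wanted, name the form, define the levels and say how patients without a further test are handled.

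The cost is a wording change to the analysis text. It needs no new data and no change to the sample size.
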